	Secondary To determine the accuracy of digital FCM in detecting and ruling out positive surgical margins on an individual margin/image level.	
	To evaluate the classification performance of FCM in differentiating between low- and high-grade prostate cancer.	
	To assess the interobserver variability in reporting of digital FCM images.	
OUTCOME MEASURES	Primary	
OUTCOINE MEASURES	Sensitivity, specificity, positive and negative predictive value of digital FCM for detection of clinically significant prostate cancer at surgical margins, with traditional H&E histopathology as the reference standard, on a per-patient basis. Clinically significant cancer is defined as Gleason score >/=7 (ISUP Grade Group >/=2).	
	Sacardam	
	Secondary Sensitivity, specificity, positive and negative predictive value of digital FCM for detection of cancer at surgical margins, with traditional H&E histopathology as the reference standard, on a per-image/margin level.	
	Area under the receiver operating characteristic curve (AUC) for cancer detection of digital FCM with traditional H&E histopathology as the reference standard.	

Short Title:	Sponsor:	Version:	Date:
IP8-FLUORESCE	ICHNT	1.2	02 April 2024

	Agreement of digital FCM with the pathology report for cancer length at margin (mm) on a margin and patient level. Agreement of digital FCM with the pathology report for cancer grade at margin (mm) on a margin and patient level. Cohen's kappa coefficient for agreement between readers (two individual histopathologists, histopathologist vs trainee histopathologist, histopathologist vs urologist).
POPULATION	Men undergoing radical prostatectomy for prostate cancer.
ELIGIBILITY	Inclusion Criteria Men undergoing radical prostatectomy at any of the study centres during the study period. All nerve sparing and non-nerve sparing cases will be included consecutively. Exclusion Criteria Men who do not consent for ex vivo tissue research. Men who are listed for salvage prostatectomy and had a previous prostate cancer treatment (radiotherapy, brachytherapy, focal therapy).
DURATION	The recruitment period will begin in August 2023 and run until the required number of cases to reach statistical power have been recruited.

Short Title:	Sponsor:	Version:	Date:
IP8-FLUORESCE	ICHNT	1.2	02 April 2024

1. INTRODUCTION

1.1. BACKGROUND

Fluorescence confocal microscopy (FCM) is an imaging technique whereby digital images of fresh tissues are produced almost instantly, without the need for time-consuming fixation techniques¹. It has been evaluated across a number of different organ systems and can accurately diagnose prostate cancer when compared to conventional histopathology^{2–5}. Intraoperative analysis of surgical margins during prostatectomy using frozen sections (NeuroSAFE)⁶ has not been widely adopted in the UK due to a number of major obstacles. FCM is cheaper, quicker, and requires less resources than NeuroSAFE and may represent a more feasible alternative. Two small, underpowered and unblinded studies have evaluated FCM for intraoperative analysis of surgical margins with promising results^{7,8}. The IP8-FLUORESCE study aims to robustly evaluate FCM in the real-time identification of positive surgical margins in radical prostatectomy specimens using a prospective, blinded, paired-cohort confirmatory design.

1.2. RATIONALE FOR CURRENT STUDY

Radical prostatectomy (RP) is an effective oncological and widely proffered approach to treating prostate cancer. There is reasonable evidence that for men with the correct indication a small to moderate survival increase is seen as long as the life expectancy is 10 to 15 years⁹. Functional outcomes are variable and high long-term rates of urinary incontinence and erectile dysfunction have been reported in the UK¹⁰. In potent patients undergoing RP, preservation of the neurovascular bundles (NVBs) may spare erectile function in 50% to 80%¹¹. Nerve-sparing RP, however, results in higher rates of positive surgical margins (PSMs), specifically in men with early extracapsular extension that is often not seen on preoperative MRI staging¹¹. Up to 50% of men with a PSM will experience biochemical recurrence (BCR) which in turn may require additional adjuvant treatment¹². PSMs have not been shown to be an independent predictor of overall survival but are considered an important surrogate for complete cancer excision. Ex vivo intra-operative assessment of PSMs using frozen section in the NeuroSAFE procedure has been shown to reduce PSMs⁶. Whether this translates to a better oncological outcome is unknown. The NeuroSAFE method may also increase the number of men suitable for nerve-sparing surgery but we do not know if this leads to improved erectile function rates. The unproven benefits of NeuroSAFE and the major cost implications of longer operating times by 60-70 minutes has prevented mainstream adoption. This is compounded by the UK-wide shortage of histopathologists¹³. While concordance between NeuroSAFE and conventional histopathology is excellent, the procedure is time-consuming, laborious, and costly, restricting its use in UK clinical practice¹⁴. This calls for a cheaper, faster and similarly accurate method of real-time PSM assessment during prostate cancer surgery: FCM is the foremost candidate of all real-time tissue imaging technologies.

Short Title:	Sponsor:	Version:	Date:
IP8-FLUORESCE	ICHNT	1.2	02 April 2024

What is FCM?

Confocal laser microscopy uses pinhole apertures in the microscope detector to reject outof-focus light, reducing blur and producing high-resolution imaging in thick tissue samples.
Fluorescence confocal microscopy uses fluorochromes to increase the cell-to-stroma
contrast. Depending on the laser wavelength, reflectance (488 nm) and fluorescence (785
nm) can be applied¹⁵. Novel confocal microscopes allow visualisation with reflectance and
fluorescence simultaneously and the traditional greyscale is digitally enhanced to provide a
two-colour scale which resembles haematoxylin and eosin (H&E) staining. FCM requires
minimal tissue preparation (typically staining samples in Acridine Orange for 10 seconds
then washing with saline) and can produce high-resolution images in less than a minute.
Scanners are portable and require only one square metre of space, and can therefore be
kept in the operating theatre or an office. Critically, the samples can be re-examined with
conventional techniques after FCM as the fluorescent dye does not alter the specimen and
tissue fixation is not required. Images can be directly uploaded to electronic patient records
for review by pathologists or trained urologists⁷.

Summary of prostate applications

FCM appears to be highly accurate when compared to traditional histological analysis across multiple organ systems¹⁶. In the setting of basal cell carcinoma (BCC), the technique is well-established, allowing for rapid identification of margins with high sensitivity and specificity in Mohs samples¹⁷. Whilst there is no Level 1a/b evidence available, a number of prospective studies have shown that FCM works in principle for the purpose of real-time prostate cancer diagnosis on biopsy core tissue^{2–5} and should be further evaluated for its application in a wider patient population. The potential application in intra-operative real-time analysis of surgical margins has only been analysed in two small studies with high probability of bias.

Rocco et al⁸ reported the first proof-of-concept study assessing FCM in determining PSMs. This study was underpowered and not blinded. It only included 24 patients of which 50% were lost to follow up. Mohs sections at the NV-adjacent-posterolateral surface on eight patients with intermediate or high-risk prostate cancer patients undergoing full-bilateral-NS robot-assisted RP (RARP) were assessed with FCM by two uro-pathologists. The samples were subsequently fixed in formalin and embedded in paraffin and analysed with H&E staining. Seven of the eight patients had negative surgical margins with 100% agreement between FCM and traditional histopathology, and complete inter-rater agreement for FCM between the two pathologists. For the patient with a PSM, a focal secondary resection was performed, allowing complete resection of the tumour.

The second study directly compared NeuroSAFE to FCM in determining PSM rates⁷. Surgical margins were assessed during 50 NS-RARP procedures in patients scheduled for NeuroSAFE and the accuracy of FCM and NeuroSAFE were compared with conventional histopathology. 96 posterolateral sections of RP specimens were evaluated. FCM identified 15 (16%) PSMs and NeuroSAFE identified 14 (15%). There was a substantial level of agreement between

Short Title:	Sponsor:	Version:	Date:
IP8-FLUORESCE	ICHNT	1.2	02 April 2024

FCM and NeuroSAFE, and the ability of both techniques to identify PSMs compared to histopathology was excellent, with high overall diagnostic accuracy. Critically, FCM required a significantly shorter procedure time than NeuroSAFE (8 vs 50 minutes). Whilst a larger sample size than the first proof-of-concept study, it was not powered to draw key conclusions. A further significant limitation of this study was the non-blinded assessment of the FCM images.

2. STUDY OBJECTIVES

Primary

To determine the accuracy of digital FCM in detecting and ruling out positive surgical margins in prostate specimens on a patient level, in patients undergoing radical prostatectomy for prostate cancer.

Secondary

To determine the accuracy of digital FCM in detecting and ruling out positive surgical margins on an individual margin/image level.

To evaluate the classification performance of FCM in differentiating between low- and high-grade prostate cancer.

To assess interobserver variability in reporting of digital FCM images.

3. STUDY DESIGN

IP8-FLUORESCE is prospective, multicentre, blinded, cohort study performed ex vivo using prostate specimens obtained during radical prostatectomy to evaluate the accuracy of FCM in determining surgical margin status. The reference standard will be an independent histology report. The Histolog® Scanner (SamanTree Medical SA, Lausanne, Switzerland) will be used to obtain FCM images. A pilot phase consisting of 5 patients will be performed to define the exact standard operating procedure (SOP) for handling and scanning of tissues.

Men undergoing RP for localised prostate cancer will have both FCM and histopathological evaluation of surgical margins. Once recruitment is complete, images will be reported blinded by an independent histopathologist trained in interpretation of FCM images.

The study is ex vivo and no deviations from standard of care will take place during the study.

Short Title:	Sponsor:	Version:	Date:
IP8-FLUORESCE	ICHNT	1.2	02 April 2024

3.1. PRELIMINARY SOP

Surgical procedure

Patients with prostate cancer diagnosed based upon suspicious MRI with associated confirmatory prostate biopsy whose case has been discussed in the locoregional multidisciplinary meeting will undergo robotic prostatectomy (RP). All cases will be robotic-assisted using the Da Vinci Xi surgical system (Intuitive Surgical, Sunnyvale, USA). Both nerve-sparing (bilateral or unilateral) and non-nerve sparing procedures will be performed depending on individual surgeon assessment of each case. RP will be performed by experienced urological surgeons across three major tertiary referral study centres. Men who consent to ex vivo tissue research through will be included.

FCM technique

The Histolog® scanner is a CE-IVD-certified scanning device with a wide-field-of-view confocal laser scanning microscope, designed for scanning large biological specimens in a clinical setting. Tissue fluorescence is excited by a laser at the wavelength of 488 nm and fluorescence emission is collected at a wavelength >500 nm. Additional post-processing is not required though an inbuilt system automatically converts them from monochromatic to purple in order to increase readability and align more closely with traditional H&E-stained images.

Prostate specimens will be removed from the abdominopelvic cavity and photographed to obtain views from each aspect in order to retain orientation during the scanning procedure. The specimens will be immersed whole in the Histolog® Dip (a fluorescent histological stain) for 10 seconds, then rinsed in 0.9% saline and transferred to the Histolog® Dish.

The specimens will be scanned whole, without the need for any tissue resection. They will be placed on the Histolog® Scanner and weighed down with a small bag of sand (process TBC during pilot phase) to increase tissue contact with scanner.

A low-resolution preview image will be acquired in 5 seconds to make a technical judgement of the completeness of the image, the presence of excess tissue, and the absence of air bubbles. If necessary, the specimen will be repositioned and a high-resolution digital image will be acquired within 50 seconds. The procedure will be performed for six margins in total for each specimen:

- Base
- Apex
- Left lateral
- Right lateral
- Posterior
- Anterior

Short Title:	Sponsor:	Version:	Date:
IP8-FLUORESCE	ICHNT	1.2	02 April 2024

The specimen will then be formalin-fixed and paraffin-embedded before undergoing formal histological assessment for margin status by a histopathologist. Clinical management of these patients will follow current standard-of-care pathways.

Outcome reporting

The histopathology slides for each patient will be digitally scanned and uploaded to a secure cloud-based server alongside the FCM images. All files will be pseudoanonymised and the server locked until the recruitment target has been reached. Once recruitment is complete, histopathology slides will be re-reported by expert independent uro-pathologists who will also report the margin status for the FCM images. They will be blinded to the margin status and the patient details in the histology report when making the FCM report, and vice versa. The histopathologist will provide the overall margin status on a per-patient level, as well as a report on a margin level, for length of cancer at the margin and highest grade (Table 1).

Table 1. Example case report form for margin status for a single patient.

	FCM Margin Status			Histopathology Margin Status		
	(0=negative, 1=positive, 2=indeterminate)	Length (mm)	Grade (highest; 3, 4, 5)	(0=negative, 1=positive, 2=indeterminate)	Length (mm)	Grade (highest; 3, 4, 5)
Base						
Apex						
Lateral (left)						
Lateral (right)						
Anterior						
Posterior						
Overall						

The recruitment target is 5 patients for the pilot phase, followed by 100 patients for the main phase. The study will run for 6 months or until the recruitment target is reached.

Short Title:	Sponsor:	Version:	Date:
IP8-FLUORESCE	ICHNT	1.2	02 April 2024

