3.2. STUDY OUTCOME MEASURES

Primary

Sensitivity, specificity, positive and negative predictive value of digital FCM for detection of clinically significant prostate cancer at surgical margins, with traditional H&E histopathology as the reference standard, on a per-patient basis. Clinically significant cancer is defined as Gleason score >/=7 (ISUP Grade Group >/=2).

Secondary

Sensitivity, specificity, positive and negative predictive value of digital FCM for detection of cancer at surgical margins, with traditional H&E histopathology as the reference standard, on a per-image/margin level.

Area under the receiver operating characteristic curve (AUC) for cancer detection of digital FCM with traditional H&E histopathology as the reference standard.

Agreement of digital FCM with the pathology report for cancer length at margin (mm) on a margin and patient level.

Agreement of digital FCM with the pathology report for cancer grade at margin (mm) on a margin and patient level.

Cohen's kappa coefficient for agreement between readers (two individual histopathologists, histopathologist vs trainee histopathologist, histopathologist vs urologist)

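### The same group of uro-pathologists reads both the FCM images and the H&E slides, and nothing in the protocol stops a reader from linking the two, so the independent reference is not secured and accuracy is open to upward bias

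*Protocol*

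**What the plan says.** Section 3 of the protocol promises that "The reference standard will be an independent histology report" and has the FCM images read, blinded, by an independent histopathologist. Section 3.1, under outcome reporting, sets out who does what: "histopathology slides will be re-reported by expert independent uro-pathologists who will also report the margin status for the FCM images".

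The same part of section 3.1 describes these safeguards:

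- Blinding in both directions: "They will be blinded to the margin status and the patient details in the histology report when making the FCM report, and vice versa".
- Pseudonymisation and a lock: "All files will be pseudoanonymised and the server locked until the recruitment target has been reached".

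It also describes how the material is kept and recorded. The slides are "digitally scanned and uploaded to a secure cloud-based server alongside the FCM images". The form carries FCM columns and histopathology columns for the same six margins and an overall row, under the caption "Table 1. Example case report form for margin status for a single patient".

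On which histology report is the reference, section 3.2 names H&E histopathology for the accuracy outcomes. For length and grade it refers to a pathology report, as in "Agreement of digital FCM with the pathology report for cancer length at margin (mm) on a margin and patient level". Every specimen also has a routine clinical margin assessment (section 3.1), and section 7.1 uses the clinical reports for the interim count of positive surgical margins (PSM).

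**The concern.** In an accuracy study the index test and the reference have to be read without knowledge of each other. When one group does both jobs, the blinding has to cover more than someone else's report: it must also cover the reader's own other read of the same case. A statement of blinding cannot do that if the reader can recall the case or trace it through a shared code or form.

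If the second read is pulled towards the first, disagreements turn into agreements. Sensitivity, specificity, and the length and grade agreement would then tend to rise together. A larger sample would not remove the effect, and the confidence interval would not show it. The point matters here because sections 1.1 and 1.2 give lack of blinding as a weakness of both earlier margin studies, and section 1.1 presents this study as the blinded, confirmatory one.

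**Working it through.** **1. What the reading plan secures.**

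| Question | Protocol |
|---|---|
| Who reads FCM? | An independent histopathologist (section 3); the uro-pathologists who re-report H&E (section 3.1) |
| Who reads H&E for the study? | The same group of uro-pathologists (section 3.1) |
| Different readers for the two modalities of one patient? | Not stated |
| Blinding between the reads? | Stated, both ways (section 3.1) |
| Reading order, interval between reads, lock on the first read? | Not stated |
| Separate code for each modality? | Not stated; pseudonymisation only |
| Server lock? | Until the recruitment target is reached, which is when reading starts |
| Which report is the reference? | Not settled between the clinical report and the re-report (sections 3 and 3.2) |

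Pseudonymisation hides who the patient is. It does not hide that two files belong to the same patient, unless the codes differ by modality. The server lock protects the period before reading, not the reading itself. Section 3.1 gives the re-report no purpose other than outcome reporting, so it is the likelier reference, but the protocol does not say so.

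**2. The plan's own figures.** Section 7.1 gives sensitivity 0.85, specificity 0.95, prevalence 30%, precision of 14 points either way, 95% confidence and 10% dropout.

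- n = z² × Se × (1 − Se) / d² = 1.96² × 0.85 × 0.15 / 0.14² = 24.99, so 25. The protocol has 27, which gives a half-width of 1.96 × √(0.85 × 0.15 / 27) = 0.135.
- 27 / 0.9 = 30, and 30 / 0.30 = 100, as stated.

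The plan's 27 is close to the formula, and this point does not change the sample size.

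**3. How much drift could matter.** Let f be the share of discordant patients whose second read moves to agree with the first. No value of f is in the documents, so it is an assumption, shown over a range.

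If the FCM call moves to the H&E call: Se′ = Se + f(1 − Se) and Sp′ = Sp + f(1 − Sp).

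If the H&E call moves to the FCM call, at prevalence 0.30, the starting shares are TP = 0.255, FN = 0.045, FP = 0.035 and TN = 0.665. Then Se′ = (TP + f·FP) / (TP + f·FP + (1 − f)·FN) and Sp′ = (TN + f·FN) / (TN + f·FN + (1 − f)·FP).

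| f | Se′ / Sp′, FCM moves | Se′ / Sp′, H&E moves |
|---|---|---|
| 0 | 0.850 / 0.950 | 0.850 / 0.950 |
| 10% | 0.865 / 0.955 | 0.865 / 0.955 |
| 25% | 0.888 / 0.963 | 0.887 / 0.963 |
| 50% | 0.925 / 0.975 | 0.924 / 0.975 |

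The gain in sensitivity is 0 at f = 0, 1.5 points at 10% and 7.5 points at 50%. The direction of drift hardly matters, so fixing the reading order alone does not close the gap.

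**4. In patients.** With 27 PSM patients, 0.85 × 27 is about 23 detected and 4 missed. Each miss turned into an agreement adds 1/27 = 3.7 points. Two of the four, the 50% case, would move 23/27 (85.2%) to 25/27 (92.6%).

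**The case against.** The strongest defence is that the protocol does address blinding. It runs in both directions, and on a natural reading that covers a reader's own other read. Files are pseudonymised, and reading waits until recruitment is complete, so about 100 patients with six FCM images each are read together, which makes recall of a single case harder. All of this stands, and it lowers the risk. It does not remove it, because no step keeps the two reads of one patient apart.

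A reader might infer more than the documents support:

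- *That one person reads both modalities of each patient.* Section 3.1 speaks of uro-pathologists in the plural and assigns both tasks to the group. A later sentence refers to the histopathologist in the singular, but that does not settle it. The arrangement is not excluded; nor is it stated.
- *That the reference is not independent and accuracy is biased upward.* Upward is the likely direction if a first read is recalled or linked. Whether that happens, and how often, cannot be derived from the protocol. If the clinical report were the reference, the problem would largely fall away.
- *That each patient's files are kept together in view of the reader.* The text establishes a shared server, no more. Table 1 is labelled an example, and a paired layout may only reflect how data are captured.
- *That the interim look changes the reference.* It uses the clinical reports only to count PSM prevalence.

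It can also be said that reading order and coding belong in a reading manual. But the protocol has already assigned the reads, and the pilot is meant to settle how specimens are handled and scanned, not how they are read. Finally, crossing readers lets between-reader H&E variation into the accuracy estimate. That is a real, though small, cost.

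**Conclusion.** The point holds as a risk that the design leaves open, not as a demonstrated bias. The protocol states blinding but fixes nothing that would secure it when the same group reads both modalities, and this sits badly with the independent reference and independent reader of section 3. It also leaves unsettled which histology report is the reference.

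The size is unknown. The gain of 1.5 to 7.5 points of sensitivity rests on the protocol's own 0.85 and on an assumed drift of 10% to 50% of discordant cases. It is zero if the blinding holds. The upper end is about half the planned precision of 14 points. The matter should be settled before reading starts, because linked reads cannot be separated afterwards by analysis.

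**What to change.** Amend section 3.1 and Table 1, with matching wording in sections 3 and 3.2:

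1. Complete and lock all FCM reads before any H&E slides are released to the readers.
2. Give each modality its own random case codes and its own random order, with the key linking them withheld from readers.
3. Split Table 1 into an FCM form and a histopathology form.
4. Where the histopathologists already planned for the kappa analysis allow, compare one reader's FCM read with another reader's H&E read for each patient, and acknowledge that between-reader H&E variation then enters the estimate.
5. Name the blinded expert H&E re-report as the single reference for the primary, length and grade outcomes. The clinical reports can still serve the interim PSM count.

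The cost is an edit to the reading plan and case report form, file re-coding, and some sequencing of reads. No further patients are needed, and no further readers where the planned ones can be paired.
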